3.4 Study Data Sources

Information on the hospital's or ward's standards of practice for PIVC management will be recorded by the PI or designee into the Hospital/Ward PIVC Therapy Standards of Practice Questionnaire.

After the subject provides his/her written informed consent, subject and PIVC-related data will be collected from the subject's medical records and by observation of the PIVC insertion site. This information will be recorded into the Individual PIVC Questionnaire.

The investigator will be responsible for ensuring that all the required data is collected in the study-specific eCRF. No subject identifiable information will be captured.

3.4.1 Study Variables

The following variables will be collected in this study:

- Hospital/Ward standards of practice for PIVC management:
 - Existence of standards of practice for PIVC management at the hospital or ward: yes/no

3M Confidential

Document Name: CLIN-PROT-ICH-US-05-331782

Clinical and Non-Clinical: CLIN-INDEX-3M-SPON-US-05-014222

- Skin antiseptic solution used prior to PIVC insertion:
 - Sterile or nonsterile normal saline
 - Isopropyl alcohol (and percent alcohol concentration)
 - Ethanol alcohol (and percent alcohol concentration)
 - Povidone iodine (and percent concentration)
 - Chlorhexidine gluconate (CHG) in alcohol (and percent CHG concentration)
 - CHG alone
 - Other (specify)
 - Not defined
- Skin antiseptic container:
 - Multi-use bottle
 - Single-use sterile container
 - Not defined
- Skin antiseptic solution applicator:
 - Non-sterile gauze or absorbent pad
 - Non-sterile cotton ball
 - Sterile gauze or absorbent pad
 - Sterile cotton ball
 - Swab sticks
 - Wipes or Wipettes
 - Other (specify)
 - Not defined
- Frequency of PIVC site rotation:
 - Every 72 hours
 - Every 96 hours
 - As clinically indicated
 - Other (specify)
 - Not defined
- Frequency of PIVC assessment:
 - Every 4 hours
 - Every 8 hours
 - Every 24 others
 - Other (specify)
 - Not defined
- Method used to access or connect the catheter or primary IV tubing:
 - Needle-based system
 - Needleless-based system
 - Access extension (side injector)
 - 3-way open female luer
 - Not defined
- Use of disinfectant cap to cover access ports, needleless caps or hubs when not in use or not connected to another IV set: yes, sometimes, no
- Cap used to protect and seal the access ports or catheter hub when no infusion is administered:

- Caps that accompany the IV tubing
- Needleless cap only
- Disinfection cap (Curos, SwabCap, other (specify))
- Caps from a syringe needle
- No cap, end is directly connected to other tubing
- Access port not covered
- Not defined
- Solution used to disinfect the access ports of the IV bag/bottle, catheter and tubing prior to attachment:
 - 70% isopropyl alcohol
 - 70% ethanol alcohol
 - CHG solution (and percent CHG concentration)
 - Other (specify)
 - Not defined
- Technique used to disinfect the access ports:
 - Single swipe
 - Twisting motion (timed or not)
 - Back and forth motion with friction (timed or not)
 - Other (specify)
 - Not defined
- Patients who receive infusion therapy through an infusion pump:
 - All patients receiving IV medication, electrolyte or solution
 - ICU patients only
 - Limited to patients receiving specific medications
 - None of the patients
 - Other (specify)
 - Not defined
- Responsible person who adds medications and electrolytes to IV infusion bottles or bags:
 - Nurse
 - Pharmacist
 - Physician
 - Nurse technician
 - Other (specify)
 - Not defined
- Environment where medications and electrolytes are added to IV infusion bottles or bags:
 - Nurses' station
 - Medication room
 - Patient's room/ward
 - Pharmacy
 - Not defined
- Socio-demographic variables:
 - Date of birth
 - Initials
 - Gender

- Individual PIVC variables:
 - Date and time of PIVC audit
 - Date and time of PIVC insertion
 - Responsibility for PIVC insertion:
 - Nurse
 - Physician
 - Nurse technician
 - Other (specify)
 - Unknown/Not documented
 - Department where PIVC was inserted:
 - Emergency department
 - Operating room
 - Intensive or Critical Care Unit (ICU)
 - General ward/clinic
 - Radiology or other procedure room
 - Ambulance/Emergency Medical System (EMS)
 - Other hospital
 - Unknown/Not documented
 - PIVC location:
 - Left or right hand
 - Left or right wrist
 - Left or right forearm
 - Left or right antecubital fossa
 - Left or right upper arm
 - Left or right foot
 - Left or right side of the head
 - Other (specify)
 - Reason for PIVC insertion:
 - IV fluids
 - IV medications
 - Blood sampling
 - Patient unstable/requiring resuscitation
 - Blood product transfusion
 - Parenteral nutrition
 - Chemotherapy
 - Unknown/Not documented
 - Other (specify)
 - Assessment of PIVC site is documented in the patient chart in the last 24 hours: yes, no
 - Site labeled with date and time of catheter insertion: yes, no.
 - Site overdue for relocation: yes, no. If yes: description for absence of relocation in medical records (yes, no)
 - Use of PIVC: continuous, intermittent

- Flush solution used to keep the PIVC open:
 - No flushing
 - 0.9% sodium chloride
 - Heparin/heparinized saline solution
 - Other (specify)
 - Not applicable (PIVC used continuously)
 - Unknown/Not documented
- IV medications and solutions infused using this PIVC within the last 24 hours:
 - Fluids without electrolytes
 - Antimicrobials
 - Analgesics
 - Sedation
 - Other (specify)
 - None
 - Unknown/Not documented
- PIVC gauge/size:
 - 14G (orange)
 - 16G (grey)
 - 18G (green)
 - 20G (pink)
 - 22G (blue)
 - 24G (yellow)
 - 26G (purple)
 - Steel needle
 - Not visible
 - Other (specify)
- PIVC and administration set (extension tubing) securement
 - Sutureless securement device
 - Sterile tape strips around PIVC
 - Non-sterile tape around PIVC
 - Non-sterile tape over PIVC dressing
 - Non-sterile tape around administration set
 - IV administration set securement device
 - Splint/bandage/tubular net
 - Site dressing only
 - Other (specify)
- IV connectors:
 - Extension tubing
 - Stopcock/3-way tap
 - Needleless connector directly attached to catheter hub
 - Cap attached to the end of the catheter
 - IV tubing directly connected to catheter
 - Other (specify)
 - None
- PIVC dressing type:
 - Tape only (type of tape: paper, plastic, soft cloth, silk, other (specify))

- Gauze and tape dressing
- IV FIX
- Transparent film dressing
- Transparent film dressing and tape
- Bordered film dressing
- No dressing
- Other (specify)

- Signs and symptoms at the PIVC site: yes, no. If yes:
 - Pain/tenderness on palpation
 - Redness > 1 cm from insertion site
 - Swelling > 1 cm from insertion site
 - Purulence
 - Itch/rash under dressing
 - Blistering/skin tears under dressing
 - Dried blood
 - Palpable hard vein cord beyond IV tip
 - Streak/red line along vein
 - Induration/hardness of tissues > 1 cm
 - Other (specify)
- Presence of any of the following clinical complications: phlebitis (grade 1-4; mechanical, chemical, infective), hematoma, ecchymosis, skin injury, local infection.
- Presence of any of the following mechanical complications: catheter dislodgement, occlusion, extravasation, infiltration (grade 1-4), leaking at the insertion site.
- Presence of any of the following quality issues: unstable PVIC, blood reflux, uncontrolled IV infusion rate, site dressing partially detached, site dressing totally detached (site exposed to environment), medical tape added to dressing edges, unclean dressing, discomfort at site with or without palpation, uncovered tubing access port, lack of visibility at the PIVC site.

3.5 Randomization and Blinding

No blinding will occur during the study. As this is an observational study of existing PIVC practice and related complications, randomization is not applicable.

3.6 Study Materials and Labeling

There are no study materials, except for the study-specific questionnaires..

3.7 Study Duration

The study is expected to be open at each participating site until a minimum of 100 PIVC sites are assessed, so that a minimum of 300 PIVCs are assessed at all three participating hospitals.

Since this is an observational, cross-sectional study, each patient's involvement in the study will have a duration of one day only.

3.8 Study Termination

3M or the Investigator has the right to discontinue the study at any time for medical and/or administrative reasons. As far as possible, this should occur after mutual consultation.

Conditions that may warrant termination of the study by 3M include, but are not limited to the following:

- Failure of the Investigator to comply with pertinent ICH and ANVISA Regulatory Guidelines.
- Insufficient adherence to protocol requirements.
- Failure of the Investigator to complete the study at an acceptable rate.
- Submission of knowingly false information from the Investigator to 3M.
- Termination of Ethics Committee approval

3.9 Investigational Material Accountability

Based on the study design and lack of intervention, no investigational material will be provided or used in this study. Only the study-specific questionnaires to document the required study information will be distributed to the investigators. The investigator must keep the completed investigational questionnaires in a secure storage area, accessible only to authorized individuals.

3.10 Protocol Modifications

3.10.1 Protocol Amendments

The party initiating an amendment must confirm it clearly in writing using the Amendment/Administrative Revision form. It must be signed and dated by 3M and, in case of a significant amendment, the Investigator. A significant amendment means one that affects the safety, rights or welfare of subjects, the scope of the investigation or the scientific quality of the study.

3M will forward any significant protocol amendments to each study site's PI, who is responsible for submitting them to the Ethics Committee for approval.

3.10.2 Protocol Deviations

A deviation is a departure from the protocol that will likely affect the safety, rights or welfare of subjects, the scope of the investigation or the scientific quality of the study.

If the study personnel fail to obtain the subject's informed consent prior to data collection, then this would be considered a protocol deviation and the local Ethics Committee should be notified.

Deviations that potentially affect data integrity or compromise the statistical analysis of the study require immediate communication to 3M. The Investigator must contact the 3M study monitor within 24 hours of occurrence. A Protocol Deviation Form must be completed by the Investigator and include the type of deviation and a description of the circumstances surrounding the deviation. A copy is sent to the 3M study monitor within 24 hours of identifying the occurrence. This kind of deviation should also be notified to the local Ethics Committee.

3.11 Computerized Systems

Computerized systems that will be used to create, modify, maintain, archive, retrieve or transmit data include, but may not be limited to:

- SAS

3M Confidential

Document Name: CLIN-PROT-ICH-US-05-331782

Clinical and Non-Clinical: CLIN-INDEX-3M-SPON-US-05-014222

- Excel
- Word
- Microsoft Outlook

4. Subject Selection

The study population will include adult patients admitted to the wards of the participating acute care hospitals that will be audited in the study. To minimize subject selection bias, all subjects will be identified and invited to participate in the study consecutively, as the auditor screens the ward on the day of the audit.

To be included in the study and for their PIVC sites to be evaluated, each patient should meet all of the inclusion criteria and none of the exclusion criteria described in the sections below. Subjects should provide written informed consent prior to any study-specific observations and data collection.

4.1 Subject Inclusion Criteria

Subjects must fulfil **all** the following inclusion criteria at the time of the audit to be included:

- Male or female subject, aged 18 years or older at the time of the study's audit of the ward;
- Subject admitted into one of the wards audited at the study site;
- Subject available for observation at the time of the audit;
- Subject with at least one inserted PIVC;
- Subject that voluntarily signed and dated the informed consent form (ICF) prior to study entry.

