3.2 Study Setting

The study is expected to be conducted at three acute care centers located in Brazil. Assessment of PIVCs insertion sites and related complications, as well as of standards of practice for PVIC management, will take place at the hospitals' general or specialty admission wards. Wards where the study procedures are not to be carried out include outpatient clinics, mental health wards, emergency wards and burn units.

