4.2 Subject Exclusion Criteria

Subjects must **not meet any** of the following exclusion criteria at the time of the audit to be included:

- Subject under treatment at the study site's outpatient clinics;
- Subject admitted into a mental health ward, emergency ward or burn unit;
- Subject awaiting transfer to another facility.

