4.3 Subject Informed Consent

The Investigator at each site must obtain a written informed consent of all subjects to participate in the study, before study-related procedures. Full and adequate information about the nature, purpose, possible risks and benefits of the study must be provided. Subjects must also be notified that they are free to discontinue their participation in the study at any time. The subjects should be given the opportunity to ask questions and allowed time to consider the information provided.

As delineated in [ResolutionNo466](#) and [PANDRH-GCPs](#), the ICF content should be briefly and clearly presented orally, and in writing, in a manner that is easy to understand, commensurate with the comprehension level of the research participants, and without coercion or unduly influencing a potential participant to enroll in the study. Specifically, the Investigator is to explain to each subject all elements of informed consent as specified in ANVISA Regulatory Guidelines.

After the explanation, the subject or representative will voluntarily sign and date the consent form if they wish to participate in the study. An original version of the consent form must be provided to the subject. Another original signed and dated version of the ICF must be

maintained in the Investigator study documentation file at all times. The process of consent and study participation, with date, must be documented in the patient record/chart.

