6.2 Statistical Methods

6.2.1 General aspects

For the purposes of the present study, the unit of analysis will be the individual PIVC sites and not the patients in which they are inserted.

Descriptive statistics will be obtained for numerical variables, including central tendency measures such as mean, median as well as the dispersion measures of standard deviation, min-max and inter-quartile range. Descriptive statistics for categorical variables will include frequencies' tabulation with counts and percentages. No imputation of missing values will be made. 95% confidence intervals will be used if applicable. The significance tests of association under exploratory analyses will be made at the 5% significance level.

Data will be presented for the overall study sample, as well by hospital and by hospital ward.

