6.2.2 Primary endpoint analysis

The prevalence of PIVC-related complications among the PIVC sites audited at the participating acute care hospitals in Brazil will be determined as follows:

- Prevalence (%) = (Number of audited PIVC sites with at least one clinical or mechanical complication ÷ Number of audited PIVC sites) x 100

The definitions of clinical and mechanical complications are detailed in Section 3.3 and Appendix I.

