6.4 Procedures to Account for Missing, Unused, and Spurious Data

Investigation of spurious and/or missing data will be discussed in the final report. Imputation of missing data will not be performed. Non-use of data will be described and justified in the final report.

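### Does the mismatch between Sections 4.1 and 4.3 on who may sign consent leave the primary denominator undefined?

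*Combined protocol and SAP*

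**What the plan says.** The last inclusion criterion in Section 4.1 is "Subject that voluntarily signed and dated the informed consent form (ICF) prior to study entry". Section 4.3 describes how consent is obtained and ends with the statement that "the subject or representative will voluntarily sign and date the consent form if they wish to participate in the study". A representative is mentioned nowhere else, and nothing says when one may act.

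The lead-in to Section 4 ties eligibility to the audit. For a patient's catheter sites to be evaluated, "each patient should meet all of the inclusion criteria and none of the exclusion criteria described in the sections below".

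Section 6.2.2 defines the primary prevalence as "Number of audited PIVC sites with at least one clinical or mechanical complication", divided by all audited sites. Section 6 names no separate analysis set. Section 6.4 adds that "Non-use of data will be described and justified in the final report", and Section 6.5 asks for the same account of any departure from the statistical plan. Section 6.2.1 fixes the level of reporting: "Data will be presented for the overall study sample, as well by hospital and by hospital ward".

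On setting, Section 3.2 states: "Wards where the study procedures are not to be carried out include outpatient clinics, mental health wards, emergency wards and burn units". Section 4.2 repeats this for patients, for example "Subject admitted into a mental health ward, emergency ward or burn unit". Neither section names intensive care, and no exclusion covers inability to consent.

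**The concern.** Taken word for word, the two sections give opposite answers for the same patient. If a representative signs, Section 4.3 is satisfied and Section 4.1 is not. Two hospitals could each follow one section in good faith and enrol different populations.

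The statistical worry comes next. The primary formula counts audited sites and does not mention eligibility. Section 3.10.2 makes missing subject consent a notifiable deviation but does not say whether the data stay in. The variable list in Section 3.4.1 has no item for who signed. If some sites were audited on a representative's signature, someone might decide whether to keep them after seeing the complication counts. Patients unable to sign may also be sicker and may have a different complication rate, so the choice could move the headline prevalence. These data are also meant to serve as the first stage of a before-and-after comparison (Sections 1.2 and 3.1), which gives the population definition some further weight.

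**Working it through.** **1. Do the other sections bar representatives?** Sections 3.3, 3.4 and 3.10.2 and the lead-in to Section 4 all refer to the subject's consent. That looks like support for a subject-only rule. But Section 4.3 uses the same generic language: it requires consent from all subjects and explanation to each subject, and then allows a representative to sign. The generic wording is therefore compatible with a representative's signature. Only Section 4.1 speaks of the subject signing, and it can be read as a one-line summary of the procedure in 4.3.

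**2. What does each reading do to the denominator?**

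- *4.1 is shorthand for 4.3.* The patient is eligible, the site is audited, and Section 6.2.2 counts it.
- *4.1 is literal.* The patient is not eligible, so under the Section 4 lead-in the site is not evaluated and appears in neither numerator nor denominator.
- *A hospital follows 4.3 and 4.1 is later held to be literal.* The site has been audited, so Section 6.2.2 counts it. Removing it would be non-use of data and would have to be described and justified under Section 6.4.

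Only the third case leaves a choice, and even there the formula gives a default.

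**3. How large could that choice be?** The plan's own total reproduces: 3 hospitals × 100 sites = 300 (Sections 3.2, 3.7 and 6.3). The documents give no number of representative-signed sites, no difference in prevalence and no expected prevalence, so the following are assumptions:

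- *r*, representative-signed sites: 3, 9, 15 or 30 of 300
- *d*, their prevalence minus that of the others: 10 or 20 percentage points
- overall prevalence: 40%, that is 120 of 300

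Shift on dropping them = −(r/300) × d. Limits: (120 − r)/(300 − r) if all of them have a complication, and 120/(300 − r) if none has.

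| r | Size of shift, d = 10 | Size of shift, d = 20 | All complicated | None complicated |
|---|---|---|---|---|
| 3 | 0.1 | 0.2 | 117/297 = 39.39%, −0.61 | 120/297 = 40.40%, +0.40 |
| 9 | 0.3 | 0.6 | 111/291 = 38.14%, −1.86 | 120/291 = 41.24%, +1.24 |
| 15 | 0.5 | 1.0 | 105/285 = 36.84%, −3.16 | 120/285 = 42.11%, +2.11 |
| 30 | 1.0 | 2.0 | 90/270 = 33.33%, −6.67 | 120/270 = 44.44%, +4.44 |

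For scale, the 95% half-width, treating sites as independent, is 1.96 × √(0.40 × 0.60/300) = 5.54 points. Clustering of sites within patients and hospitals would normally widen it. Only the corner case of 30 sites, all complicated, goes beyond it. A larger assumed share of 60 in 300 with d = 20 gives (60/300) × 20 = 4.0 points, still inside.

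**4. By hospital.** If 15 such sites all fell in one hospital of 100, d = 20 would move that hospital's figure by (15/100) × 20 = 3.0 points, against a half-width of 1.96 × √(0.24/100) = 9.6 points.

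**The case for a change.** The strongest case for acting is that the contradiction is plain, the repair is cheap, and the shorthand reading is nowhere stated. One aligned sentence, plus a line in Section 6.2.2 tying the denominator to eligibility, would close off any later choice. Patients unable to sign are conceivable, since intensive care is not an excluded setting and sedation is a listed infusion category in Section 3.4.1. The later before-and-after comparison also needs the same population rule at both stages.

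Part of this stands. The two sentences do differ, and the sponsor and ethics committees may wish to make them agree. The consent form is not in the reviewed text and may already settle the intent.

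The statistical part does not carry through. No section says that an intensive care unit will be audited: Section 3.2 speaks of general or specialty wards, and the investigator selects them. Sedation given in the past 24 hours does not establish incapacity at audit. The added line in 6.2.2 would write down what the Section 4 lead-in already implies. The missing data item does not lose the information, because signed forms are retained (Section 10.4), the consent process is recorded in the chart (Section 4.3), and the monitor has access to both (Sections 4.3.1 and 7). A separate estimate for representative-signed sites would say little: at 40% its half-width is 1.96 × √(0.24/15) = 24.8 points with 15 sites and 17.5 with 30. Consistency between the two stages is a matter for the later study, which can adopt whatever rule was applied here.

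**Conclusion.** This is a clerical slip between a summary criterion and the procedure it summarises. It comes with a gap in Section 6 that analysts would fill in the obvious way: audited sites are those in patients admitted under Section 4, and anything left out is reported. If every hospital requires the subject's own signature, the prevalence is sound for patients who signed for themselves. If every hospital accepts representatives, those sites are counted. Neither reading produces a wrong figure, and the primary result is a descriptive proportion with no hypothesis test.

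A problem would need hospitals to diverge, training, the pilot site and monitoring to miss it, and a material number of such sites with a markedly different prevalence. The documents show none of these. Under the assumed differences of 10 to 20 points for 3 to 30 sites, the shift is 0.1 to 2.0 points against a half-width of about 5.5. The counts, the differences and the 40% are all assumptions. The textual mismatch is certain, but its effect on the primary prevalence is not demonstrated, and no change to the plan follows.
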